**P15-743 (HCV RWE) \_ STATISTICAL ANALYSIS PLAN \_ final 2.0 \_ 02 Feb 2018**

Similar to table 1.14.1, the following tables will be constructed:

- Table 1.14.2 Co-infections (overall – HCV genotype groups)
- Table 1.14.3 Co-infections (overall – Child Pugh classes groups)
- Table 1.14.4 Co-infections (overall – prior treatment groups)

These tables will be repeated for each treatment group:

- Table 1.14.X Co-infections (treatment group X – HCV genotype and subtype groups)
- Table 1.14.X Co-infections (treatment group X – Child Pugh classes groups)
- Table 1.14.X Co-infections (treatment group X – prior treatment groups)

Also the table 1.14.1 will be repeated for the target population and the safety population:

- Table 1.14.X Co-infections
- Table 1.14.X Co-infections

---

 Patients will be divided into subgroups by HCV genotype (1a or 1b). Patients with genotypes combination will be divided into separate subgroups.  
 Patients will be divided into subgroups by Child Pugh classes A, B and C.  
 Patients will be divided into subgroups by presence of prior treatment: “INF”, “RBV”, “DAA”, “Treatment-experienced all” and “Naïve”. Patients with prior treatment components combination will be divided into separate subgroups.

 If the target population and the safety population will be equal then the tables for the target population will be presented only and it will be noted in the footnotes in presented tables.

P15-743 (HCV RWE) \_ STATISTICAL ANALYSIS PLAN \_ final 2.0 \_ 02 Feb 2018

AbbVie LLC  
P15-743 (HCV RWE)  
**Table 1.15.1 Co-infections. HIV most recent test results**  
The core population  
Page X of X

|                                    | ABBVIE REGIMEN + RBV
12 weeks
(N = XX) | ABBVIE REGIMEN - RBV
12 weeks
(N = XX) | Overall
(N = XX) |
|------------------------------------|--|--|---------------------|
| CD4 T-cell count                   |  |  |                     |
| n                                  | XX   | XX   | XX                  |
| less 50                            | XX (XX.X)                                    | XX (XX.X)                                    | XX (XX.X)           |
| 50-199                             | XX (XX.X)                                    | XX (XX.X)                                    | XX (XX.X)           |
| 200-349                            | XX (XX.X)                                    | XX (XX.X)                                    | XX (XX.X)           |
| 350-500                            | XX (XX.X)                                    | XX (XX.X)                                    | XX (XX.X)           |
| >500                               | XX (XX.X)                                    | XX (XX.X)                                    | XX (XX.X)           |
| HIV-RNA test                       |  |  |                     |
| Result                             |  |  |                     |
| n                                  | XX   | XX   | XX                  |
| undetectable                       | XX (XX.X)                                    | XX (XX.X)                                    | XX (XX.X)           |
| detectable                         | XX (XX.X)                                    | XX (XX.X)                                    | XX (XX.X)           |
| Below limit of quantification      |  |  |                     |
| Yes                                | XX (XX.X)                                    | XX (XX.X)                                    | XX (XX.X)           |
| No                                 | XX (XX.X)                                    | XX (XX.X)                                    | XX (XX.X)           |
| Quantitative result (unit measure) |  |  |                     |
| n                                  | XX   | XX   | XX                  |
| Mean                               | XX.X   | XX.X   | XX.X                |
| SD                                 | XX.XX  | XX.XX  | XX.XX               |
| Median                             | XX.X   | XX.X   | XX.X                |
| IQR                                | XX.X   | XX.X   | XX.X                |
| Min                                | XX   | XX   | XX                  |
| Max                                | XX   | XX   | XX                  |

N: the number of subjects in the core population.  
n: the number of valid measurements.  
Percentages are calculated from the number of subjects in the core population.

Program code, date, time

Data extracted: DD.MM.YYY

Similar to table 1.15.1, the following tables will be constructed:

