9.4.1.1 Inclusion Documentation

The following will be documented:

- Demographic information
 - Interleukin 28B (IL28B) genotypes
- CHC disease characteristics
 - Year of diagnosis and mode of infection
 - Stage of liver fibrosis
- CHC treatment history
 - Naïve or experienced
 - If experienced, most recent prior therapy and outcome
- Relevant medical history, co-morbidities and co-infections
- Concomitant medication, see 9.4.1.5
- ABBVIE REGIMEN ± RBV
- Laboratory data

Key clinical chemistry	Remarks
▪ ALT (alanine-aminotransferase)	including upper limit of normal (ULN),
▪ AST (aspartate-aminotransferase)	including ULN, AST to platelet ratio index (APRI) and Fibrosis-4 Score/Index (FIB-4)* will be calculated
▪ γ-GT (gamma-glutamyltransferase)	
▪ Total bilirubin	
▪ Albumin	
▪ Creatinine	creatinine clearance [#] will be calculated
▪ AFP	
Key hematology	
▪ Hb (Hemoglobin)	
▪ Platelets	
▪ Prothrombin time	or international normalized ratio (INR)
Virology	
▪ HCV genotype and subtype	
▪ HCV RNA	quantitative/ qualitative HCV RNA by polymerase chain reaction (PCR) test, see 9.4.1.4
HIV-infected patients only	
▪ CD 4 count (cluster of differentiation 4)	most recent assessment
▪ HIV RNA	in copies/mL

*derived from patient's age, ALT, AST and platelets

[#]by Cockcroft-Gault-Formula based on creatinine, gender, age and weight

Confidential Information

No use or disclose outside AbbVie is permitted without prior written authorization from AbbVie

Version 3.0 (22 Apr 2015) – country v 1.0 dated 26.06.2015

Page 25 of 61

- Patient questionnaires, see table 2 and 9.4.1.6
- PAM-13
- Treatment related health care resource utilization

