## **7 Statistical considerations**

### **7.1 Standard descriptive statistics**

The data of continuous type will be presented with following statistics:  $n$  (the number of subjects with non-missing data), mean, median, standard deviation (SD), interquartile range (IQR), minimum and maximum values. In quantitative tests the values less than LLoQ will be replaced to 1/2 of LLoQ, the values more than ULoQ will be replaced to ULoQ.

The data of categorical type (including clinical evaluations) will be presented with  $n$  (the number of subjects with no missing data), frequencies and percentages. Unless otherwise specified, percentages by categories will be based on the number of subjects with no missing data.

Confidence intervals will be calculated for all effectiveness endpoints and questionnaires results.

The number of decimals for each descriptive statistical value will be determined by the following rules:

- mean, median and IQR: +1 decimal place compared to the analyzed variable values;
- standard deviation: +2 decimal places compared to the analyzed variable values;
- minimum and maximum values: the same as for the analyzed variable values;
- percentages (including CI) will be rounded to one decimal place.

The maximum number of decimal places in the statistical report is four. If some descriptive statistical value has more than four decimal places after above mentioned rules application, this value will be rounded to four decimal places .

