### 8.5 Concurrent Illnesses and Medical Conditions

Medical history will be coded using the MedDRA version 20.0 (or further updating) and summarized by system organ class (SOC) and preferred term (PT) according to Data MATRIX LLC SOP [3] and will be presented in listings and tables.

Tables with descriptive statistics in accordance with section 7.1 will be presented for the following parameters, which are evaluated on baseline visit:

- presence of co-infection with other relevant diseases;
  - HIV characteristics:
    - CD4 T-cell count (for HIV co-infected patients);
    - HIV-RNA test results (for HIV co-infected patients);
  - liver and/or CHC related co-morbidities;
  - other co-morbidities.
- All corresponding listings will be presented.

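### Tables 1.15.x calculate CD4 and HIV-RNA percentages from the whole core population, although these data exist only for HIV-infected patients and SAP 8.5 with 7.1 calls for patients with data

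*SAP*

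**What the plan says.** - **Who has the data.** Protocol 9.4.1.1 lists CD4 count and HIV RNA under "HIV-infected patients only". SAP 8.5 likewise labels both items as applying to HIV co-infected patients.
- **Which denominator the text sets.** SAP 8.5 introduces its list with "Tables with descriptive statistics in accordance with section 7.1 will be presented for the following parameters, which are evaluated on baseline visit". SAP 7.1 then says: "Unless otherwise specified, percentages by categories will be based on the number of subjects with no missing data".
- **Which denominator the shell sets.** The footnote to Table 1.15.1 reads "Percentages are calculated from the number of subjects in the core population". The table is repeated by genotype, Child-Pugh class and prior treatment, within each treatment group, and for the target and safety populations.
- **What else the shell prints.** Table 1.15.1 has a row for n, the number of valid measurements, in the CD4 block, the HIV-RNA result block and the quantitative block. The *Below limit of quantification* block has none.
- **Neighbouring tables.** Table 1.8.1 (cirrhosis characteristics) and Table 1.14.1 (co-infections) carry the same footnote. SAP 8.4 refers the cirrhosis items to section 7.1. SAP 8.5 defines the co-infection variable as "presence of co-infection with other relevant diseases".

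**The concern.** A CD4 band or an HIV-RNA result is not applicable to a patient without HIV. If such patients sit in the denominator, the percentage no longer answers the question that the row asks, namely how HIV-infected patients are distributed over CD4 bands and viral-load results. It becomes a mixture of that distribution and HIV prevalence.

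This bears on the secondary objective of collecting information on co-morbidities in the Russian population. A reader comparing the regimen columns could take a difference in HIV prevalence for a difference in HIV status among those infected. The same question arises for Table 1.8.1 if its Child-Pugh components were recorded only in patients with cirrhosis.

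**Working it through.** The plan gives no figure for HIV prevalence, HIV control, cirrhosis share or testing rates. All rates below are assumptions. N = 158 is the planned size in SAP 4.2, used only as an illustrative column total.

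**Formula.** Let N be the number of core-population patients in a column, h the number with an HIV result, and c the number in a category.

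- Footnote: 100 × c/N
- SAP 7.1: 100 × c/h
- Relation: 100 × c/N = (100 × c/h) × (h/N)

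The scaling factor h/N is the same for every category in a block.

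**Table 1.15.1, one worked case.** Take h = 8, with 7 undetectable and 1 detectable.

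- Factor: 8/158 = 5.1%
- Undetectable: 7/158 = 4.4% printed, against 7/8 = 87.5%
- Detectable: 1/158 = 0.6% printed, against 1/8 = 12.5%
- Sum of the two printed figures: 8/158 = 5.1%, not 100%

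**Range over other assumed counts (N = 158).**

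| HIV-infected with result | Undetectable | Printed under footnote | With valid n |
|---|---|---|---|
| 3 | 2 | 1.3% | 66.7% |
| 5 | 4 | 2.5% | 80.0% |
| 8 | 7 | 4.4% | 87.5% |
| 16 | 14 | 8.9% | 87.5% |
| 32 | 26 | 16.5% | 81.25% |

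**Comparing columns.** Suppose 80% of HIV-infected patients are undetectable in both regimen columns, but HIV prevalence is 5% in one and 15% in the other. The footnote prints 0.80 × 5% = 4.0% and 0.80 × 15% = 12.0%. With valid n, both columns show 80%.

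**Table 1.8.1, two cases.**

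- If every patient has the components recorded, h = N, the factor is 1, and the footnote and SAP 7.1 agree.
- If only cirrhotic patients have them, with an assumed 60% and 10% cirrhotic in two columns and 15% with ascites among the cirrhotic in each, the footnote prints 0.15 × 60% = 9.0% and 0.15 × 10% = 1.5%. Valid n gives 15% in both.

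The documents do not settle which case applies. The table title and the Protocol annex, which presents Child-Pugh as a scale of cirrhosis severity, point to the second. Bilirubin, albumin and prothrombin time are on the baseline list for all patients (Protocol 9.4.1.1), and SAP 8 and 9 use Child-Pugh class to stratify the whole core population; both point to the first.

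**Table 1.14.1.** The rows are diagnoses and n is the count in each. Eight recorded hepatitis B diagnoses give 8/158 = 5.1%, the ordinary prevalence of a recorded diagnosis. If only 70% had been tested, the figure among the tested would be 8/(0.70 × 158) = 7.2%, but the documents show neither untested patients nor a field for testing status.

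**The case against.** The strongest defence is that SAP 7.1 allows exceptions where something else is specified, and the footnote specifies something else, openly. That would settle the matter if SAP 8.5 were silent, but it refers these same tables to section 7.1. The footnote sentence also recurs across many shells, which suggests standard text rather than a choice made for HIV data. Where the SAP wants valid measurements as the base in a shell, it says so, as in Table 4.5.2. A mismatch between text and shell remains.

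The second defence is that n is printed, so a reader who sees n = 8 and 7 undetectable can recompute the percentage. This stands and limits the harm. It does not cover the *Below limit of quantification* block, which has no n of its own, and a table should not print percentages that its readers must correct. The quantitative HIV-RNA summary is unaffected.

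The third defence is that a baseline table is meant to show case mix. That is right for Table 1.14.1, which reports how many patients have HIV. Table 1.15.1 describes those who have it.

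**Conclusion.** The point holds for Tables 1.15.x. The documents restrict the data to HIV-infected patients and the SAP text sets valid data as the base, yet the footnote divides by everyone. The printed percentages shrink by the factor h/N: from 87.5% to 4.4% in the assumed case of 8 HIV-infected patients among 158. The size depends wholly on HIV prevalence, which the documents do not give. For Tables 1.8.x the distortion is possible but not established; valid n is the base that SAP 8.4 and 7.1 call for and is safe in either case.

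Four stronger readings are tempting and are not supported:

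- **HIV control is understated.** Every category shrinks by the same factor, including detectable HIV RNA and low CD4 bands, so no direction follows.
- **Columns differ by case mix alone.** That requires equal distributions among the infected (or the cirrhotic) in each column, which is an assumption made only for illustration above.
- **Table 1.8.1 results exist only for cirrhotic patients.** No section says so.
- **Co-infection prevalence in Table 1.14.1 is understated.** A recorded diagnosis over the core population is a legitimate prevalence, and nothing shows that patients went untested.

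These are descriptive baseline tables. The SVR12 estimate and its confidence interval are not affected.

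**What to change.** 1. **Tables 1.15.x:** replace the footnote so that the denominator is HIV-infected patients with a valid result, which is the printed n. Add an n row to the *Below limit of quantification* block. Keep the column N as a header only.
2. **Tables 1.8.x:** use the number of patients with the component recorded as the denominator.
3. **Repeats:** apply the same denominators wherever these two tables are repeated, including the target and safety populations.
4. **Tables 1.14.x:** leave the denominator as it is.

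The cost is a footnote and denominator edit in two table families and one added row, with no new data. The downside is that the percentages will rest on visibly smaller n.

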**P15-743 (HCV RWE) \_ STATISTICAL ANALYSIS PLAN \_ final 2.0 \_ 02 Feb 2018**

- Table 1.15.2 Co-infections. HIV most recent test results (overall – HCV genotype groups)
- Table 1.15.3 Co-infections. HIV most recent test results (overall – Child Pugh classes groups)
- Table 1.15.4 Co-infections. HIV most recent test results (overall – prior treatment groups)

These tables will be repeated for each treatment group:

- Table 1.15.X Co-infections. HIV most recent test results (treatment group X – HCV genotype and subtype groups)
- Table 1.15.X Co-infections. HIV most recent test results (treatment group X – Child Pugh classes groups)
- Table 1.15.X Co-infections. HIV most recent test results (treatment group X – prior treatment groups)

Also the table 1.15.1 will be repeated for the target population and the safety population :

- Table 1.15.X Co-infections. HIV most recent test results
- Table 1.15.X Co-infections. HIV most recent test results

---

 Patients will be divided into subgroups by HCV genotype (1a or 1b). Patients with genotypes combination will be divided into separate subgroups.  
 Patients will be divided into subgroups by Child Pugh classes A, B and C.  
 Patients will be divided into subgroups by presence of prior treatment: “INF”, “RBV”, “DAA”, “Treatment-experienced all” and “Naïve”. Patients with prior treatment components combination will be divided into separate subgroups.

 If the target population and the safety population will be equal then the tables for the target population will be presented only and it will be noted in the footnotes in presented tables.

P15-743 (HCV RWE) \_ STATISTICAL ANALYSIS PLAN \_ final 2.0 \_ 02 Feb 2018

Prior medications

AbbVie LLC  
P15-743 (HCV RWE)  
**Table 1.16.1 Prior Medications for CHC**  
The core population  
Page X of X

| 4th level, chemical subgroup
Preferred/Generic Level | ABBVIE REGIMEN + RBV
12 weeks
(N = XX)
n (%) / E |               | ABBVIE REGIMEN - RBV
12 weeks
(N = XX)
n (%) / E |               | Overall
(N = XX)
n (%) / E |
|---|---|---------------|---|---------------|----------------------------------|
|   | XX (XX.X) /XX   | XX (XX.X) /XX | XX (XX.X) /XX   | XX (XX.X) /XX |                                  |
| Total [1]   | XX (XX.X) /XX   | XX (XX.X) /XX | XX (XX.X) /XX   | XX (XX.X) /XX | XX (XX.X) /XX                    |
| XXXXXXXXXXXXXXXXXXXXXXXXXXXX                            | XX (XX.X) /XX   | XX (XX.X) /XX | XX (XX.X) /XX   | XX (XX.X) /XX | XX (XX.X) /XX                    |
| XXXXXXXXXXXXXXXXXXXXXXXXXXXX                            | XX (XX.X) /XX   | XX (XX.X) /XX | XX (XX.X) /XX   | XX (XX.X) /XX | XX (XX.X) /XX                    |
| XXXXXXXXXXXXXXXXXXXXXXXXXXXX                            | XX (XX.X) /XX   | XX (XX.X) /XX | XX (XX.X) /XX   | XX (XX.X) /XX | XX (XX.X) /XX                    |
| ...   | ...   | ...           | ...   | ...           | ...                              |
| XXXXXXXXXXXXXXXXXXXXXXXXXXXX                            | XX (XX.X) /XX   | XX (XX.X) /XX | XX (XX.X) /XX   | XX (XX.X) /XX | XX (XX.X) /XX                    |
| XXXXXXXXXXXXXXXXXXXXXXXXXXXX                            | XX (XX.X) /XX   | XX (XX.X) /XX | XX (XX.X) /XX   | XX (XX.X) /XX | XX (XX.X) /XX                    |
| ...   | ...   | ...           | ...   | ...           | ...                              |
| ...   | ...   | ...           | ...   | ...           | ...                              |

N: number of subjects in the core population.  
n: number of subjects within a specific category. Percentages are calculated as 100 x (n/N).  
#E: number of prior medications events reported.  
Prior medications are any medications taken prior to the date of first dose of study treatment/ICF sign.  
Prior medications were coded using the World Health Organisation (WHO) Anatomical Therapeutic Chemical (ATC) classification system version XX.  
The ATC groups are sorted by n (%). Preferred names are sorted by n (%) within ATC group.  
Each subject is only counted once per preferred name and once per ATC group.

Program code, date, time  
Data extracted: DD.MM.YYYY

Similar to table 1.16.1, the following tables will be constructed:

**P15-743 (HCV RWE) \_ STATISTICAL ANALYSIS PLAN \_ final 2.0 \_ 02 Feb 2018**

- Table 1.16.2 Prior Medications for CHC. HIV most recent test results (overall – HCV genotype groups)
- Table 1.16.3 Prior Medications for CHC. HIV most recent test results (overall – Child Pugh classes groups)
- Table 1.16.4 Prior Medications for CHC. HIV most recent test results (overall – prior treatment groups)

These tables will be repeated for each treatment group:

- Table 1.16.X Prior Medications for CHC. HIV most recent test results (treatment group X – HCV genotype and subtype groups)
- Table 1.16.X Prior Medications for CHC. HIV most recent test results (treatment group X – Child Pugh classes groups)
- Table 1.16.X Prior Medications for CHC. HIV most recent test results (treatment group X – prior treatment groups)

Also the table 1.16.1 will be repeated for the target population and the safety population :

- Table 1.16.X Prior Medications for CHC. HIV most recent test results
- Table 1.16.X Prior Medications for CHC. HIV most recent test results

---

 Patients will be divided into subgroups by HCV genotype (1a or 1b). Patients with genotypes combination will be divided into separate subgroups.  
 Patients will be divided into subgroups by Child Pugh classes A, B and C.  
 Patients will be divided into subgroups by presence of prior treatment: “INF”, “RBV”, “DAA”, “Treatment-experienced all” and “Naive”. Patients with prior treatment components combination will be divided into separate subgroups.

 If the target population and the safety population will be equal then the tables for the target population will be presented only and it will be noted in the footnotes in presented tables.

**P15-743 (HCV RWE) \_ STATISTICAL ANALYSIS PLAN \_ final 2.0 \_ 02 Feb 2018**

**Concurrent medications**

Similar to tables 1.16.\*, the following tables will be constructed:

Table 1.17.1 Concurrent Medications for CHC

Table 1.17.2 Concurrent Medications for CHC. HIV most recent test results (overall – HCV genotype groups)

Table 1.17.3 Concurrent Medications for CHC. HIV most recent test results (overall – Child Pugh classes groups)

Table 1.17.4 Concurrent Medications for CHC. HIV most recent test results (overall – prior treatment groups)

Table 1.17.X Concurrent Medications for CHC. HIV most recent test results (treatment group X – HCV genotype and subtype groups)

Table 1.17.X Concurrent Medications for CHC. HIV most recent test results (treatment group X – Child Pugh classes groups)

Table 1.17.X Concurrent Medications for CHC. HIV most recent test results (treatment group X – prior treatment groups)

Table 1.17.X Concurrent Medications for CHC. HIV most recent test results

Table 1.17.X Concurrent Medications for CHC. HIV most recent test results

 If the target population and the safety population will be equal then the tables for the target population will be presented only and it will be noted in the footnotes in presented tables.  
 Patients will be divided into subgroups by HCV genotype (1a or 1b). Patients with genotypes combination will be divided into separate subgroups.

 Patients will be divided into subgroups by Child Pugh classes A, B and C.

 Patients will be divided into subgroups by presence of prior treatment: “INF”, “RBV”, “DAA”, “Treatment-experienced all” and “Naïve”. Patients with prior treatment components combination will be divided into separate subgroups.

